12.1.5 Secondary Response Criteria (CHOI for CT and EORTC for [¹⁸F]-FDG-PET)

CHOI criteria determines response based on changes in size and tumor density (Table 17) [33]. This is of particular importance in GIST, as tumors often initially respond to selective KIT inhibition with inflammation and a paradoxical increase in size with a decrease in density prior to decreasing in size.

Table 17: CHOI Criteria:

Modified CT Response Evaluation Criteria	
Response	Definition
CR	Disappearance of all lesions No new lesions
PR	A decrease in size* of $\geq 10\%$ or a decrease in tumor density (HU) $\geq 15\%$ on CT No new lesions
SD	No obvious progression of nonmeasurable disease Does not meet the criteria for CR, PR, or PD No symptomatic deterioration attributed to tumor progression
PD	An increase in tumor size of $\geq 10\%$ and does not meet criteria of PR by tumor density (HU) on CT New lesions New intratumoral nodules or increase in the size of the existing intratumoral nodules

Abbreviations: CR, complete response; PR, partial response; HU, Hounsfield unit; CT, computed tomography; SD, stable disease; PD, progression of disease; RECIST, Response Evaluation Criteria in Solid Tumors.
*The sum of longest diameters of target lesions as defined in RECIST.

To evaluate for early tumor response based on FDG-PET, the EORTC criteria [34]. The EORTC FDG-PET response criteria is defined as the following:

Progressive metabolic disease (PMD) is classified as an increase in [¹⁸F]-FDG tumor SUV of greater than 25% within the tumor region defined on the baseline scan, visible increase in the extent of [¹⁸F]-FDG tumor uptake (>20% in the longest dimension) or the appearance of new [¹⁸F]-FDG uptake in metastatic lesions.

Stable metabolic disease (SMD) is classified as an increase in tumor [¹⁸F]-FDG SUV of less than 25% or a decrease of less than 15% and no visible increase in extent of [¹⁸F]-FDG tumor uptake (>20% in the longest dimension).

Partial metabolic response (PMR) is defined as a reduction of a minimum of 25% in tumor [¹⁸F]-FDG SUV after 4 weeks of treatment.

Complete metabolic response (CMR) is defined as complete resolution of [¹⁸F]-FDG uptake within the tumor volume so that it was indistinguishable from surrounding normal tissue.

12.1.6 Not evaluable (NE)

When no imaging/measurement is done at all at a particular time point, the patient is considered not evaluable (NE) at that time point.

12.1.7 Early death

If the patient has NO repeat tumor assessments following initiation of study therapy resulting from the death of the patient due to disease or treatment, it is considered early death.

MEMORIAL SLOAN-KETTERING CANCER CENTER
IRB PROTOCOL

IRB#: 14-140 A (7)

12.1.8 Symptomatic Deterioration

Patients with global deterioration of health status requiring discontinuation of treatment without objective evidence of disease progression at that time will be recorded as “symptomatic deterioration”. Every effort should be made to document objective progression even after discontinuation of treatment.

12.1.9 Confirmation of response

Complete or partial response may only be claimed if the criteria for each are met at a subsequent time point (≥ 4 weeks later) in studies with a primary endpoint that include response rate. When response rate is a secondary endpoint, confirmation is NOT required.

12.1.10 Special note on target lesions that become “too small to measure”

While on study, all lesions (nodal and non-nodal) recorded at baseline should have their actual measurements recorded at each subsequent evaluation, even when very small (e.g. 2mm). However, sometimes, lesions or lymph nodes which are recorded as target lesions at baseline become so faint on CT scan that the radiologist may not feel comfortable assigning an exact measure and may report them as being “too small to measure.” When this occurs, it is important that a value be recorded on the D2M form. If it is the opinion of the radiologist that the lesion has likely disappeared, the measurement should be recorded as 0 mm. If the lesion is believed to be present and is faintly seen but too small to measure, a **default value** of 5 mm should be assigned.

12.1.11 Evaluation of best overall response within 32 weeks of combination treatment based on Table 18:

Table 18:

Target lesions	Non-target lesions	New lesions	Overall response
CR	CR	No	CR
CR	Non-CR/non-PD	No	PR
CR	Not evaluated	No	PR
PR	Non-PD or not all evaluated	No	PR
SD	Non-PD or not all evaluated	No	SD
Not all evaluated	Non-PD	No	NE
PD	Any	Yes or No	PD
Any	PD	Yes or No	PD
Any	Any	Yes	PD

* If a CR is truly met at first time point, then any disease seen at a subsequent time point, even disease meeting PR criteria relative to baseline, makes the disease PD at that point (since disease must have appeared after CR). However, sometimes “CR” may be claimed when subsequent scans suggest small lesions were likely still present and in fact the patient had PR or SD, not CR at the first

MEMORIAL SLOAN-KETTERING CANCER CENTER
IRB PROTOCOL

IRB#: 14-140 A (7)

time point. Under these circumstances, the original CR should be changed to PR or SD and the best response is PR or SD.

12.1.12 Duration of response

Defined as the time measurement criteria are first met for CR/PR until the first date that recurrent or progressive disease is objectively documented (taking as reference for progressive disease the smallest measurement recorded on study).

12.1.13 Duration of stable disease

Measured from the start of the treatment until the criteria for progression are met, taking as reference the smallest sum on study (if the baseline sum is the smallest, this is the reference for calculation of PD). For the Phase II portion, start of treatment is defined as the start of the imatinib lead-in period.

12.1.14 Progression-Free Survival (PFS)

PFS is defined as the period from start of study treatment until recurrent or progressive of disease (POD) is objectively documented (taking as reference for progressive disease the smallest measurement recorded on study), death, or date of last contact. For the Phase II portion, start of treatment is defined as the start of the imatinib lead-in period.

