4.2 Intervention

Patients who meet the eligibility criteria will be treated with the combination therapy of BGJ398 and imatinib. In the phase Ib portion of the study, patients will receive imatinib at 400 mg once daily and BGJ398 at the standard 3+3 escalation doses for 21 days on, 7 days off (treatment schedule A)(Table 1). Using treatment schedule A, if dose level 1 to -2 is identified as the MTD and concern exists regarding therapeutic activity of BGJ398 at this dose level, expansions with higher dose levels (1 to 3) may be considered at the MSKCC PI's discretion, with modification of the treatment schedule. In this setting BGJ398 will be administered daily for one week followed by 3 weeks off and imatinib will be taken daily throughout the 4 week cycle period (treatment schedule B). In the phase II portion of the study, patients will receive imatinib at 400 mg once daily (standard of care first line imatinib dose) and BGJ398 at the RP2D and treatment schedule identified in the phase Ib portion of the study. One cycle is 28 days. If no progression of the tumor is seen, patients will continue on therapy. Those patients who have progression of disease will proceed directly to second line therapy as per standard of care. For Phase II, study personnel will attempt to collect survival status for all patients after the end-of-study visit every 3 months via telephone, email, or other method for up to 3 years.

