12.0 CRITERIA FOR THERAPEUTIC RESPONSE/OUTCOME ASSESSMENT

12.1 Antitumor Effect – Solid Tumors

During the treatment period, patients will be evaluated prior to treatment and re-evaluated for response every 8 weeks for four scans. Patients will then be imaged approximately every 12 weeks until disease progression is noted. If a patient has a durable response of > 2 year, patients can be imaged every 6 months. Response and progression will be evaluated in this study using the new international criteria proposed by the revised Response Evaluation Criteria in Solid Tumors (RECIST) guideline (version 1.1) [32]. Changes in the largest diameter (unidimensional measurement) of the tumor lesions and the shortest diameter in the case of malignant lymph nodes are used in the RECIST. Choi response criteria as outlined in GIST will be used as a secondary response [33]. In addition, patients will be evaluated by FDG-PET prior to treatment and re-evaluated for response 3 weeks after the combination treatment based on the EORTC criteria[34]. This will also be used as secondary response.

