12.1.15 Overall Survival (OS)

OS is defined as the observed length of life from study entry to death or the date of last contact.

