Duration of Follow Up: Patients will be followed for toxicities 4 weeks after last dose or until death, whichever occurs first. Patients removed from study for unacceptable adverse events will be followed until resolution or stabilization of the adverse event. For Phase II, study personnel will attempt to collect survival status for all patients after the end-of-study visit every 3 months via telephone, email, or other method for up to 3 years.

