Response rate (RECIST 1.1) will be determined as the proportion of patients evaluable for efficacy (defined as patients who receive at least one dose of the combination regimen) who have complete response or partial response defined by the RECIST 1.1 with a one-sided 90% confidence interval (CI) provided. Patients missing post baseline assessment of response will be considered non-responders for the primary endpoint at that time point.

The steady state serum imatinib trough levels will be obtained and evaluated in the two-week imatinib lead in phase (two samples/patient) and in the combination therapy phase (2 samples/patient) from all patients in the Phase II portion of the trial. We will evaluate the effects of BGJ398 on imatinib steady state trough levels by comparing the values at these two time points (before and after lead in period). We will compare the ranges we obtain with the ranges reported by Demetri et al JCO 2009 and assess whether the effects are considered subtherapeutic, therapeutic, or

MEMORIAL SLOAN-KETTERING CANCER CENTER
IRB PROTOCOL

IRB#: 14-140 A (7)

supra-therapeutic. This analysis may inform future trials with this combination and will not change the dose that will be given in the combination regimen.

The secondary endpoints of the phase 2 portion include:

- (1) RR by CHOI criteria. It will be determined as the proportion of patients evaluable for efficacy who have complete response or partial response defined by the CHOI criteria with a two-sided 95% CI provided.
- (2) RR by EORTC criteria. It will be determined as the proportion of patients evaluable for efficacy who have complete response or partial response defined by the EORTC criteria with a two-sided 95% CI provided.
- (3) Progression free survival and Overall Survival. PFS and OS will be calculated using a Kaplan-Meier estimate among all patients enrolled. They are defined from the start of imatinib treatment, i.e. the lead in period is included in this endpoint. Patients on the Phase II portion who stop study prior to receiving a dose of BGJ398 for reasons unrelated to progression (e.g. intolerance to imatinib) will be censored at the time of withdrawal. Patients who have not had the event of interest by the end of the study will be censored at the time of last follow-up.
- (4) Resectability rate. It will be calculated by the proportion of Phase II patients who have completed 1 cycle of treatment who have resection of their disease with a two-sided 95% CI provided.

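### Phase II PFS is censored at last contact or last follow-up instead of the last tumour assessment, so patients who leave without progression can be credited with unscanned time (minor: secondary endpoint)

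*Combined protocol and SAP*

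**What the plan says.** Section 12.1.14 ends PFS when progression is "objectively documented (taking as reference for progressive disease the smallest measurement recorded on study), death, or date of last contact". Section 12.1.15 uses the same closing term for survival: "OS is defined as the observed length of life from study entry to death or the date of last contact". For Phase II, Section 14.0 covers PFS and OS with one censoring sentence: "Patients who have not had the event of interest by the end of the study will be censored at the time of last follow-up". Neither *last contact* nor *last follow-up* is defined.

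Contact after leaving is described in Section 13.0, under its Duration of Follow Up heading: "study personnel will attempt to collect survival status for all patients after the end-of-study visit every 3 months", for up to 3 years. Section 4.2 repeats this, and Table 11 footnote l uses the verb contact for the same call.

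Imaging is described in Section 12.1: "During the treatment period, patients will be evaluated prior to treatment and re-evaluated for response every 8 weeks for four scans", then "Patients will then be imaged approximately every 12 weeks until disease progression is noted". Section 9.0 keeps the 8-weekly scans going for 32 weeks even if treatment is interrupted. After that, Section 9.0 and Table 11 footnote f tie scans to cycle days. Table 11 marks tumour measurements in the off-study column, and footnote c places that visit 4 weeks after removal. Nothing later is listed.

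Patients who stop before their first BGJ398 dose for reasons other than progression are censored at withdrawal (Section 14.0), so this point does not concern them.

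**The concern.** Progression can be found only by looking for it. A patient who leaves for toxicity, withdrawal, non-compliance or after being rendered disease free (Section 13.0) may answer survival calls for three years without a scan. If the censoring date is the last such call, the patient stays in the PFS risk set at each later event time, and only death can register as an event. The curve then sits too high, by an amount that grows with the share who leave.

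The trial has one arm, so no control group shares the shift. PFS can only be read against the 20 to 24 months quoted for imatinib alone in Sections 1.0 and 3.1.1. Two analysts following the same text could also report different PFS from the same data.

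**Working it through.** **Stated figures.** The plan gives no PFS figure to reproduce. Its one design calculation, for response rate, does reproduce: with X ~ Binomial(44, p), P(X ≥ 25 | 0.45) = 0.0775 (stated 0.08) and P(X ≥ 25 | 0.65) = 0.901 (stated type II error 0.1). It does not involve PFS.

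**Inputs from the plan.** Median PFS 22 months (midpoint of 20-24); accrual over 24 months; scans at weeks 10, 18, 26 and 34 from the start of lead-in, then every 12 weeks; off-study visit 4 weeks after exit; contact for up to 36 months.

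**Assumptions not in the plan.** Exit rates of 5% to 30%; exits uniform over months 1-24 or 1-12 and unrelated to prognosis; exponential PFS; median post-progression survival 30 months; cut-off at month 60. The exit range is plausible but not estimated. On imatinib alone, 5% stopped for adverse events (Section 3.3.2). On BGJ398 alone, (10 + 12 + 1 + 1)/94 = 26% stopped for reasons other than progression or death (Section 11.1.2.1). Those were different populations.

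**Reference value.** The last scan by month 24 is at week 94, or 21.6 months. Then 2^(-21.6/22) = 0.506, and deaths between scans bring it to about 0.504.

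**Hand check, off-study scan counted.** With S(v) = 2^(-v/22), the share of patients assigned an exit whose progression falls after the off-study visit but would have been seen by week 94 is

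(1/23) × ∫ from 1.92 to 21.62 of [S(v) − S(21.62)] dv = (1/23) × [31.74 × (0.9413 − 0.5060) − 19.70 × 0.5060] ≈ 0.167.

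At 20% assigned an exit this is 0.20 × 0.167 = 3.3 points if none of these patients die before month 24. Deaths count as events, so the true shift is smaller.

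**Simulation** (600,000 patients per scenario, contact to 36 months). Shift in 24-month PFS, in points:

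| Assigned an exit | Months 1-24, off-study scan | Months 1-12, off-study scan | Months 1-24, no off-study scan | Months 1-12, no off-study scan |
|---|---|---|---|---|
| 5% | +0.7 | +1.1 | +0.8 | +1.3 |
| 10% | +1.3 | +2.3 | +1.7 | +2.7 |
| 20% | +2.7 | +4.6 | +3.3 | +5.3 |
| 30% | +4.0 | +7.0 | +5.1 | +8.0 |

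An assigned exit takes effect only if it comes before progression is documented. The +2.7 at 20% agrees with the hand ceiling of 3.3.

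**Precision.** √(0.504 × 0.496/44) = 0.075; the mean Greenwood standard error over simulated trials of 44 is about 7.4 points.

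**Other readings.**
- Scans carried to week 32 despite removal: +0.7 to +4.4 (months 1-24).
- Contact lapsing 3 months after exit: 0 to +1.7.
- Censoring at the off-study visit: −0.6 to +0.6.
- Imaging continued to progression after removal: 0.

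**Censoring at the last scan instead.** With exits unrelated to prognosis, the error is at most 0.2 points, or 0.8 if the off-study scan is counted. With informative exits at 20% (months 1-24, off-study scan counted), the error against the last-contact rule is −2.0 against +1.5 if the leavers' hazard halves, and +1.6 against +4.3 if it doubles.

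**The case against.** The best defence is that this is an undefined term and not a demonstrated error. The Section 14.0 sentence speaks of patients without the event by the end of the study, while the survival calls come after the end-of-study visit and collect vital status only. A statistician could fairly read last follow-up as follow-up for progression, and the shift then almost vanishes. Section 12.1 also says imaging goes on until progression, and Section 12.1.8 asks for every effort to document progression after discontinuation for symptomatic deterioration.

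Much of this stands, and it is why the effect is stated as conditional. It does not remove the point. Section 12.1.14 says last contact, the OS term, and the calendar uses contact for the survival call. The imaging sentence sits in a paragraph limited to the treatment period, and Section 12.1.8 covers only one kind of leaver.

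The size also needs restraint. Full contact to 36 months is a ceiling, because the plan only promises an attempt. If half the leavers had contact for only about a month after exit (an assumption), the shift at 20% (months 1-24) falls to +1.3 with an off-study scan.

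A reader might infer that PFS will be overstated by 5 to 8 points, or by more than a standard error. The documents do not support that. It needs high exit rates, mostly early, near-complete contact and, to exceed one standard error, no off-study assessment. Table 11 marks tumour measurements at that visit. The mark is not conclusive, since footnote f spells out a radiology duty only for removal for progression, but it cannot be ignored.

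**Conclusion.** Wrong as written, but minor. The text sets a PFS censoring date that need not be a tumour assessment and that, read literally, can fall up to three years after the last one. With the off-study assessment counted, the upward shift in 24-month PFS is about +0.7 to +4.0 points for 5% to 30% assigned an exit in months 1-24. It reaches about +7 if all exits fall in the first year, and about +8 if the off-study scan is also missing. The standard error is about 7.4 points. The median is unchanged at 5-10% exits. These sizes rest on assumed exit rates and timing and on sustained contact; the direction holds under the literal reading, and other readings give close to zero.

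Nothing here touches the primary decision of more than 24 responders in 44, and no PFS test is planned. A reader might infer that the trial's efficacy conclusion is biased; the documents do not support that.

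**What to change.** In Sections 12.1.14 and 14.0, censor Phase II PFS at the last evaluable tumour assessment, including the off-study one, for patients without documented progression or death. Split the shared sentence in Section 14.0 so that date last known alive applies to OS only. State in advance how a death after a long unscanned gap is counted. Reconcile Section 12.1 with the calendar on whether imaging continues after removal without progression.

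Keep the last-contact rule as a sensitivity analysis and tabulate exits by reason. This matters because last-scan censoring is not free of bias when exits relate to prognosis. For better-prognosis leavers, such as those rendered disease free, it errs low by about as much as the current rule errs high.

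The cost is wording only, since scan dates are already collected. The standard error of 24-month PFS rises from about 7.4 points to 7.7, 7.9 or 8.2 at 10%, 20% or 30% assigned an exit.

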12.1.15 Overall Survival (OS)

OS is defined as the observed length of life from study entry to death or the date of last contact.

13.0 CRITERIA FOR REMOVAL FROM STUDY

Patients will be removed from study when any of the criteria listed below applies. The reason for study removal and the date the patient was removed must be documented in the EDC system. Patients on the Phase II study may be replaced if they come off study for reasons other than progressive disease prior to receiving their first dose of BGJ398. Unless otherwise stated, patients will be included in the safety and/or efficacy analysis as described in Section 14.

A dose interruption of ≥ 28 days will require the patient to be discontinued from the study (with the exception of patients who undergo surgery). Local procedures (e.g. surgery, embolization) are permitted on this trial a) if clinically indicated or b) if response to therapy converts the patient into a surgical candidate. All drugs will be held for at least one week prior to the local procedure. Patients will resume therapy when deemed clinically safe, but no sooner than 1 week and no later than 5 weeks after the procedure. If a patient falls out of this window, consideration should be had for withdrawal from the study based on clinical reasons for the delay. Patients who have had a local procedure will be allowed to remain on the study if they have measurable disease (RECIST 1.1) after the procedure. Patients who are rendered disease free will be taken off the study and can be considered for adjuvant imatinib per standard of care. Conversion to resectability rate will be a secondary endpoint.

MEMORIAL SLOAN-KETTERING CANCER CENTER
IRB PROTOCOL

IRB#: 14-140 A (7)

Duration of Therapy: In the absence of treatment delays due to adverse events, treatment may continue until one of the following criteria applies:

- Disease progression,
- Intercurrent illness that prevents further administration of treatment,
- Unacceptable adverse event(s),
- Patient decides to withdraw from the study, or
- General or specific changes in the patient's condition render the patient unacceptable for further treatment in the judgment of the investigator.
- Inability of the patient to comply with the requirement of the protocol for treatment or evaluation.

Duration of Follow Up: Patients will be followed for toxicities 4 weeks after last dose or until death, whichever occurs first. Patients removed from study for unacceptable adverse events will be followed until resolution or stabilization of the adverse event. For Phase II, study personnel will attempt to collect survival status for all patients after the end-of-study visit every 3 months via telephone, email, or other method for up to 3 years.

14.0 BIOSTATISTICS

This is a multi institution single arm phase Ib/II trial to evaluate the clinical safety and efficacy of imatinib and BGJ398 in patients with advanced Gastrointestinal Stromal Tumors. Patients in the Phase Ib portion of the trial are required to have metastatic and or locally advanced GIST that has been treated with imatinib. Patients on the Phase II portion of the study are required to have advanced GIST and not have received any prior systemic therapy (untreated/treatment naïve).

Phase 1b Portion Study Design and Endpoint Assessment

The primary endpoint of the phase 1b portion of this study is to determine the maximum tolerated dose (MTD) and treatment schedule of BGJ398 administered in combination with imatinib in patients with GIST. The phase 1b will be pursued in standard 3+3 format, based on toxicities encountered during the first cycle of therapy.

The dose escalation schema is listed in Table 1. Dose escalation will proceed within each cohort according to Table 2. The first three patients will be enrolled at Dose Level 1. If dose level 1 is not found to be tolerable, then the next cohort will be enrolled at dose level -1. If dose level -1 is not found to be tolerable, then the next cohort will be enrolled at dose level -2. If dose level -2 is not found to be tolerable, then the study may be terminated based on discussions with the MSKCC Principal Investigator. If 0 or 1 of 6 patients experience a DLT on dose level 3, this will be the RP2D unless a lower dose is selected based on chronic tolerance of the combination and pharmacokinetic data. Lower dose levels may be expanded and an RP2D lower than the MTD may be selected based on safety and chronic tolerance considerations by the MSKCC Principal Investigator. If dose level 1 to -2 is identified as the MTD and concern exists regarding therapeutic activity of BGJ398 at this dose level, expansions with higher dose levels (1 to 3) may be considered at the MSKCC PI's discretion, with modification of the treatment schedule. When the RP2D is found, any patients from the Phase Ib portion of the study who remain on therapy below the MTD may have their BGJ398 dose increased to the MTD at the treating physician's discretion.

MEMORIAL SLOAN-KETTERING CANCER CENTER IRB PROTOCOL

IRB#: 14-140 A (7)

The secondary endpoints of the phase 1b portion are (1) Response Rate (RR) defined by RECIST 1.1 criteria and by CHOI criteria, (2) Progression Free Survival (PFS), (3) Clinical Benefit Rate (CBR) at 32 weeks, and (4) BGJ398 pharmacokinetic parameters, such as area under the curve (AUC) and maximum concentration (C_{max}). RR will be estimated as the proportion of patients who have complete response or partial response for each criterion. PFS will be calculated using Kaplan-Meier estimate among all patients enrolled at each dose level. Patients who have not experienced the event of interest by the end of the study will be censored at the time of the last follow-up. Plasma concentrations of BGJ398 will be analyzed at multiple time points and expressed as a mean +/- SE.

The phase 1b portion of the study will have a minimum sample size of 6 patients and a maximum of 30. We expect to accrue approximately 2 patients each month, and hence expect to finish the phase 1b portion of the study in approximately 9-15 months.

Evaluable patients for safety analysis include all patients who have received one dose of imatinib plus BGJ398. Patients who stop therapy before Cycle 2, Day 1 for reasons other than toxicity will be replaced in the Phase I study for the purposes of evaluating the DLT. Evaluable patients for efficacy include all patients who have received one dose of imatinib plus BGJ398. Patients who are missing an assessment of response post baseline will be considered non-responders for that time point.

Patients on the Phase I portion of the study will not be included in the final efficacy analysis due to differences in the eligibility criteria in the two phases.

Phase 2 Portion Study Design and Endpoint Assessment

The primary endpoint of the phase II portion of the study is to assess Response Rate (CR+PR, RECIST 1.1) after 32 weeks of combination therapy. In order to detect a 20% improvement in the RR over imatinib alone (unacceptable rate of 45%; acceptable rate of 65%), 44 Phase II patients will be enrolled. At the end of the study, if > 24 patients have had a documented response by RECIST 1.1, the study will be considered positive and the treatment regimen will be considered worthy of further investigation. The study design is based on an exact Binomial test and has a one-sided type I error of 0.08 and a type II error of 0.1.

We expect to accrue 2 patients each month, and hence expect to finish the phase 2 portion of the study in 24 months.

Response rate (RECIST 1.1) will be determined as the proportion of patients evaluable for efficacy (defined as patients who receive at least one dose of the combination regimen) who have complete response or partial response defined by the RECIST 1.1 with a one-sided 90% confidence interval (CI) provided. Patients missing post baseline assessment of response will be considered non-responders for the primary endpoint at that time point.

The steady state serum imatinib trough levels will be obtained and evaluated in the two-week imatinib lead in phase (two samples/patient) and in the combination therapy phase (2 samples/patient) from all patients in the Phase II portion of the trial. We will evaluate the effects of BGJ398 on imatinib steady state trough levels by comparing the values at these two time points (before and after lead in period). We will compare the ranges we obtain with the ranges reported by Demetri et al JCO 2009 and assess whether the effects are considered subtherapeutic, therapeutic, or

MEMORIAL SLOAN-KETTERING CANCER CENTER
IRB PROTOCOL

IRB#: 14-140 A (7)

supra-therapeutic. This analysis may inform future trials with this combination and will not change the dose that will be given in the combination regimen.

The secondary endpoints of the phase 2 portion include:

- (1) RR by CHOI criteria. It will be determined as the proportion of patients evaluable for efficacy who have complete response or partial response defined by the CHOI criteria with a two-sided 95% CI provided.
- (2) RR by EORTC criteria. It will be determined as the proportion of patients evaluable for efficacy who have complete response or partial response defined by the EORTC criteria with a two-sided 95% CI provided.
- (3) Progression free survival and Overall Survival. PFS and OS will be calculated using a Kaplan-Meier estimate among all patients enrolled. They are defined from the start of imatinib treatment, i.e. the lead in period is included in this endpoint. Patients on the Phase II portion who stop study prior to receiving a dose of BGJ398 for reasons unrelated to progression (e.g. intolerance to imatinib) will be censored at the time of withdrawal. Patients who have not had the event of interest by the end of the study will be censored at the time of last follow-up.
- (4) Resectability rate. It will be calculated by the proportion of Phase II patients who have completed 1 cycle of treatment who have resection of their disease with a two-sided 95% CI provided.

For the purpose of exploratory studies, the phase 2 portion includes the phenotypic (by IHC), genetic, transcriptomic, epigenetic, and pharmacodynamic characterization of the tumors as correlative endpoints. Twenty patients are planned to have mandatory paired biopsies (pre and post treatment), and the remaining patients will provide optional biopsies if funding is identified. This sample size provides 80% power to detect a standardized difference of 0.55 assuming 2 sided one sample paired t test at 10% significance level. The variable of interest will be change in protein levels.

The analysis of the exploratory studies is planned as follows.

- 1) ETV1 protein level by western blot (WB) as a continuous variable. The change of ETV1 protein level (before vs. after the combination therapy) will be recorded as up, down, and no-change (categorical response). It will be tabulated with the percentages provided. It will be correlated with response using the Fisher's exact test.
- 2) ETV1-dependent transcriptome (expression profile of ETV1-dependent gene targets) by nanostring. The expression change of ETV1 target genes (before vs. after the combination therapy) will be correlated with clinical response using the Wilcoxon rank test. The outcome will be a composite score (based on gene expression level and directionality of the changes), and it is continuous variable.
- 3) Cell proliferation (Ki-67) and apoptosis (cleaved caspase-3) by IHC. Descriptive statistics will be provided. These variables are continuous.
- 4) MAP kinase pathway and other pathways downstream of KIT and FGF signaling using standard antibodies (phospho-ERK, phospho-KIT, phospho-MEK, phospho-AKT, etc) by IHC. Descriptive statistics will be provided.
- 5) KIT/PDGFRα mutational status in matched tumor biopsy specimens collected prior to therapy, after combination therapy and upon disease progression. FGFR and FGF2 expression on tumor

MEMORIAL SLOAN-KETTERING CANCER CENTER IRB PROTOCOL

IRB#: 14-140 A (7)

samples by IHC analyzed as a binary covariate and FGF2 ligand levels in collected serum by ELISA analyzed as a continuous covariate.

- 6) Protein expression of FGF2, sVEGFR1, sVEGFR2, VEGF-A, -C, -D, cKIT, PLGF, and Tie2 in tumor tissues utilizing commercially available immunoassay kits. This will be a continuous variable.
- 7) Expression of genes implicated in GIST pathogenesis and signaling, including KIT, ETV1, FGFR1, -2, -3, and -4; DUSP6, SPRY2, and SPRY4 will be analyzed as a continuous covariate. Changes before and after treatment will be assessed and correlated with clinical response.

In most of the above studies, we are interested in looking at changes in expression levels, protein measurements, or mutation status before and after treatment. The correlative endpoints described above will be correlated with response (binary outcome defined as CR+PR using RECIST 1.1). These analyses are exploratory in nature and no adjustment for multiple comparisons will be made.

